Scientific rationale:	
The role of aspirin in the prevention of not only colorectal cancer but also oesophageal adenocarcinoma is already accepted in epidemiological studies (19 - 22). Although aspirin is already being used prophylactically in premalignant colorectal lesions, a study of its application to BM is urgently needed. PPIs are used widely but their efficacy in chemoprevention is unclear and if there is an effect the most cost-effective dose is not known. Esomeprazole is arguably the leading agent in its class.
	
Clinical rationale:	
Conventional clinical risk factors for BA have not been proven in randomised controlled studies, although males have an excess risk of oesophageal adenocarcinoma compared with females at a ratio of 3 to 1 (6 - 16). In the absence of proven stratification, surveillance of all cases of BM is required; this is neither feasible nor cost effective (17). Primary prevention strategies should be aimed at reducing the initiation and malignant degeneration of BM by pharmaceutical manipulation of the oesophageal environment.
	

	Potent acid suppressing drugs and aspirin for chemoprotection have the greatest applicability.	
Primary Endpoint:	A composite primary endpoint of all-cause mortality and conversion to adenocarcinoma and conversion to high grade dysplasia.	
Secondary Endpoints:	
 
• All-cause mortality
 
• Conversion to oesophageal adenocarcinoma
 
• Conversion to high grade dysplasia
 
• Death from oesophageal cancer
 
• Cost/oesophageal adenocarcinoma prevented
 
• Cost/life year saved
 
• Molecular markers to be identified at the end of the trial and used during analyses of collected blood and/or tissue samples
 
• Cost/quality adjusted life saved
 
• Formation of new tumours
 
• Composite endpoint of all-cause mortality and conversion to adenocarcinoma and conversion to high grade dysplasia according to gender
 
	
Study Design:	This is a pragmatic, national, multicentre, phase III, randomised 2x2 factorial controlled trial of low or high dose esomeprazole with or without low dose aspirin for 8-10 years	
Patient Numbers:	2513	
Target Population:	Patients with circumferential Barrett's metaplasia of at least 1cm in length ( $\geq$ C1M1) or a tongue of Barrett's metaplasia of at least 2cm in length ( $\geq$ COM2)	

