Anti-reflux surgery has been advocated for patients with BM but it is not first line therapy due to issues of fitness for surgery and peri-operative mortality rate for surgery. It is also clear that anti-reflux surgery has at most a modest effect on cancer prevention (2). Other forms of surgical intervention including endoscopic mucosal resection and laser therapy are at present carried out in too few centres and by too few people to be able to be exploited reproducibly in a national study in the near future.

The majority of adenocarcinomas in the oesophagus in the community are not diagnosed in surveillance programs. The average life expectancy in the UK for males is 73 years and for females 77 years. At these ages the commonest cause of death is ischaemic heart disease and cerebrovascular or peripheral vascular disease (42). The average age of presentation of patients with BA is 69 years. Therefore chemoprevention aims to prolong survival or delay onset of the cancer by 4 years in males and 8 years in females to allow other 'morbid diseases' to intervene naturally.

AspECT is a chemoprevention trial of acid suppression and aspirin in patients with Barrett's oesophagus. This study will allow the validation of several surrogates including biomarkers and clinical parameters. Aspirin is an effective chemoprotective agent in a number of cancers of the gastrointestinal tract. Continuous acid suppression therapy is well tolerated, has extremely low morbidity and mortality, and is available readily in every centre in the UK. These two treatments are unlikely to 'neutralise' the real benefits of each other in the majority of patients as the drugs act independently and their effects will be additive and possibly complementary. In addition, the use of these two drugs together may help decrease the side effects of aspirin intervention alone, especially in men. PPIs will be required for symptom control of reflux and aspirin may have additional benefits in reducing colorectal cancer and cardiovascular events. While the main study concentrates on males we will assess a smaller cohort of females in the integrated women's AspECT study (WASP). By doing so we will be able to address genetic and environmental reasons why males develop more oesophageal adenocarcinoma than females.

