To assess whether intervention with PPI and/or aspirin induces changes in the expression of molecular markers for BA. To assess the genomics of aspirin sensitivity (efficacy and side effects)	
 
Molecular markers to be identified at the end of the trial and used during analyses of collected blood and/or tissue samples
 
	End of trial

To assess how quality of life is affected by the different treatments	
 
Cost/quality adjusted life saved
 
	End of trial
To assess what the biological risk factors are for cardiac disease and aspirin resistance	
 
Molecular markers to be identified at the end of the trial and used during analyses of collected blood and/or tissue samples
 
	End of trial
To assess gender differences in outcomes	
 
A composite endpoint of all-cause mortality and conversion to adenocarcinoma and conversion to high grade dysplasia
 
All-cause mortality
 
Conversion to oesophageal adenocarcinoma
 
Conversion to high grade dysplasia
 
Death from oesophageal cancer
 
	End of trial
Tertiary/Exploratory Objectives	Endpoints	
To assess aspirin's role on the development of colorectal adenomas and cancer	New tumour	End of trial
To collect and bank samples for use in future ethically approved studies	Not applicable	Not applicable

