2.7 Definition of Primary and Secondary Outcomes

Primary outcome is

- Time from randomisation date to conversion from Barrett's metaplasia to high grade dysplasia (event), or to adenocarcinoma of the oesophagus (event) or time to death from all causes (event) or time to last follow-up (no event)

I.e. the time is noted as the time from date of randomisation to high grade dysplasia, adenocarcinoma of the oesophagus or death, whichever is the earlier, with the survival time coded as an event. For patients who do not have one of these events of interest, the time from randomisation to date of last follow-up is calculated and the survival time coded as a censored event.

Secondary outcomes are

- Time from randomisation date to conversion from Barrett's metaplasia to high grade dysplasia (event) or time to last follow-up (no event) or event that precludes getting high grade dysplasia (for example death) (no event)
- Time from randomisation date to progression from Barrett's metaplasia to adenocarcinoma of the oesophagus (event) or time to last follow-up (no event) or event that precludes getting adenocarcinoma of the oesophagus (for example death) (no event)
- Time from randomisation date to death from all causes (event) or time to last follow-up (no event)
- Time from randomisation date to death from oesophageal cancer (event) or time to last follow-up (no event) or death from a cause other than oesophageal cancer (no event)
- Molecular markers to be identified at the end of the trial and used during analyses of collected blood and/or tissue samples
- Cost per oesophageal adenocarcinoma prevented

AspECT

A phase III randomised study of Aspirin and Esomeprazole chemoprevention in Barrett's metaplasia

Funded by CR-UK, MRC, UHL and NCI

ISRCTN No.85156844

- Cost per life year saved
- Molecular markers to be identified at the end of the trial and used with samples collected across time along with treatment information
- Cost per quality adjusted life saved
- Cardiac event from SAE (our best data on cardiac disease) and new tumours (a marker of aspirin resistance)
- For gender secondary, same outcome as for primary

AspECT

A phase III randomised study of Aspirin and Esomeprazole chemoprevention in Barrett's metaplasia

Funded by CR-UK, MRC, UHL and NCI

ISRCTN No.85156844

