8.5 Pre-specified Subgroup Analysis

The analysis applies to males and females (planned to be 500) combined but will be repeated on males only and on just the females.

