8.8 Supporting information

The withdrawal rates from aspirin and PPI will be described as well as the dose of drug taken at time points throughout the trial.

9. Analysis to address secondary aims

There are many secondary aims so these will be described under each aim

- To assess whether intervention with aspirin results in decreased high-grade dysplasia, in decreased all cause mortality, in decreased adenocarcinoma oesophageal cancer incidence, and in decreased cause-specific mortality when each is considered separately

ANALYSIS: As for primary using the AFT model. As for primary using COX model for all cause mortality. For the COX model for high grade dysplasia, adenocarcinoma oesophageal cancer incidence and cause-specific mortality a competing risks approach will be used since there are expected to be many competing deaths for these endpoints.

For oesophageal cancer, as a sensitivity, the analysis will be rerun including all oesophageal cancers rather than just adenocarcinomas.

- To assess whether intervention with high dose PPI results in decreased high-grade dysplasia, in decreased all cause mortality, in decreased oesophageal cancer incidence and in decreased cause-specific mortality when each is considered separately

ANALYSIS: As for primary using the AFT model. As for primary using COX model for all cause mortality. For the COX model for high grade dysplasia,

AspECT

A phase III randomised study of Aspirin and Esomeprazole chemoprevention in Barrett's metaplasia

Funded by CR-UK, MRC, UHL and NCI

ISRCTN No.85156844

adenocarcinoma oesophageal cancer incidence and cause-specific mortality a competing risks approach will be used since there are expected to be many competing deaths for these endpoints.

For oesophageal cancer, as a sensitivity, the analysis will be rerun including all oesophageal cancers rather than just adenocarcinomas.

- Are there clinical and molecular risk factors than can be identified in BM for the development of BA?

ANALYSIS: Variables to be specified at the end of the trial. These variables of interest will be added to the accelerated failure time model with the event oesophageal adenocarcinoma and those found to be significant will be reported. The variables will also be considered in the competing risk COX approach.;

- What is the cost effectiveness of aspirin and/or PPI treatment in the prevention of BA?

The analysis will not be undertaken by CSM; to be analysed by [name]. Information from protocol:

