An economic analysis will be undertaken which compares the mean per patient cost of the alternative trial arms using resource use data collected in the trial and appropriate UK unit costs. Differential costs could then be related to conversion to BA. To increase the value to decision makers, the economic data collected in the trial could be synthesised with other evidence by relating long-term (lifetime) health service costs to long-term quality-adjusted life expectancy. The analysis would be based on a state transition model, which would characterise how patients progress from BM to dysplasia and to BA competing risk of death. The annual cost and health-related quality of life associated with each stage of the disease will be estimated using trial data collected and literature. In addition, some limited data collection in appropriate non-trial patients would be undertaken. Assessments will be completed at baseline and every two years at the time of endoscopy.

- To assess whether intervention with PPI and/or aspirin induces changes in the expression of molecular markers for BA. To assess the genomics of aspirin sensitivity (efficacy and side effects)

ANALYSIS: Based on analysis of the samples, this aim will be carried out after the end of the trial under a separate analysis plan.

- To assess how quality of life is affected by the different treatments.

It was not possible to collect quality of life across time and so this secondary cannot be completed.

AspECT

A phase III randomised study of Aspirin and Esomeprazole chemoprevention in Barrett's metaplasia

Funded by CR-UK, MRC, UHL and NCI

ISRCTN No.85156844

- We will also assess what the biological risk factors are for cardiac disease and aspirin resistance.

Cardiac disease will be ascertained from SAE. The risk factors to be tested are hypercholesterol, family history of cardiac disease, patient history of cardiac disease, hypertension, diabetes or smoking. A logistic model predicting cardiac disease using these factors will be built. To consider aspirin resistance, a logistic model predicting cardiac disease in those taking aspirin will be built and described.

These 2 models will be repeated for the data from the time of the new tumour questions using cancer instead of cardiac disease.

- To assess if gender is prognostic for conversion or survival

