ANALYSIS: Using the survival time calculated for the primary objective, a logrank test to assess the effect of gender with both males and females in the sample will be reported in a table as for the primary objective. Create an AFT model looking at the gender effect adjusting for age, length of Barrett's and presence of intestinal metaplasia so that there is a time ratio with 95% confidence interval for the gender effect. Repeat with a Cox model if assumptions valid. Redo both of these models with treatment also included.

Exploratory aim

To assess aspirin's role on the development of colorectal adenomas and cancer

Use as outcome the time to colorectal cancer or colorectal adenoma. Using a logrank test, consider if aspirin use is prognostic.

To collect and bank samples for use in future ethically approved studies

To be analysed under other protocols and analysis plans.

And the exploratory uses of the data

- Describe Barrett's length over repeat biopsies and investigate a change in length from baseline to 2 years between treatment groups.

ANALYSIS: For all patients, assess if Barrett's metaplasia length shows a trend with time using repeated measures anova.

Using the baseline and 2 year length, compare the Barrett's length difference between treatment groups using paired ttest.

- Can intervention with aspirin result in a lower stage of adenocarcinoma ?
Can intervention with PPI result in a lower stage of adenocarcinoma ?

ANALYSIS: Chi square trend test on the following tables

AspECT

A phase III randomised study of Aspirin and Esomeprazole chemoprevention in Barrett's metaplasia

Funded by CR-UK, MRC, UHL and NCI

ISRCTN No.85156844

	No aspirin	Aspirin
None		
Stage I		
Stage II		
Stage III		
Stage IV		

	Low PPI	High PPI
None		
Stage I		
Stage II		
Stage III		
Stage IV		

Note: this ignores the different follow-up times

- Does adjustment for oesophagectomy, ablation therapy, endoscopic mucosal resection change the treatment effect ?

ANALYSIS: Within the multivariate AFT and COX models, add time dependent variables for the above and note the new treatment effect.

- Is the event rate different for those previous users of aspirin who were not randomised to it compared to previous users who continued with aspirin as their randomised treatment?

ANALYSIS: Kaplan-Meier curve and Logrank of the previous users of aspirin who were not randomised to it versus those randomised to aspirin.

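### Protocol section 3 lists five endpoints for the gender objective; the SAP compares men and women on the composite alone, which cannot separate conversion from death

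*SAP*

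**What the plan says.** The objective is "To assess gender differences in outcomes". The documents attach different endpoints to it:

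- **Protocol section 3** lists five: the composite, all-cause mortality, conversion to oesophageal adenocarcinoma, conversion to HGD, and death from oesophageal cancer.
- **Protocol synopsis** lists one: "Composite endpoint of all-cause mortality and conversion to adenocarcinoma and conversion to high grade dysplasia according to gender".
- **SAP 2.7** lists one: "For gender secondary, same outcome as for primary".
- **SAP section 9** words the aim as "To assess if gender is prognostic for conversion or survival". The analysis begins "Using the survival time calculated for the primary objective, a logrank test to assess the effect of gender", followed by AFT and Cox models on the same time variable, first without and then with treatment.

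Protocol 1.2 links the women's cohort to the "genetic and environmental reasons why males develop more oesophageal adenocarcinoma than females". SAP 2.4 gives generalisability as the reason for the planned 500 women.

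**The concern.** The composite counts HGD, adenocarcinoma and death from any cause as one event. Men may do worse than women on it because they convert more, because they die more of other causes, or both. One hazard ratio or time ratio cannot tell these apart, and the aim in SAP section 9 names both conversion and survival. If the SAP is followed exactly, four comparisons listed in Protocol section 3 are not made, and neither document gives a reason. At stake is how a secondary, non-randomised comparison can be interpreted. The aspirin and PPI comparisons do not depend on it.

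**Working it through.** **1. Does another planned analysis supply the missing comparisons?**

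- SAP 8.5: the analysis "will be repeated on males only and on just the females". This compares treatments within a sex, not men with women. SAP 7 says the whole analysis may be repeated by sex. That is optional and could give event counts and curves by sex, but no test or estimate of the sex difference.
- SAP 8.6: the gender-adjusted AFT and Cox models are sensitivity analyses of the primary outcome, so they also use the composite.
- SAP section 9, risk factors for adenocarcinoma: AFT and competing-risks Cox models with adenocarcinoma as the event. Gender could enter, but the covariates are "Variables to be specified at the end of the trial" and only those found significant are to be reported. HGD and the two mortality endpoints are not covered.

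No pre-specified male–female comparison exists for the four endpoints.

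**2. Inputs for the illustration**

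- 2012 men and 501 women (Protocol section 2): 80.1% and 19.9%.
- Death 1.16% per year; adenocarcinoma 0.85% per year (Protocol 13.2, SAP 2.5.3). The second reproduces: 0.6 × 0.98 + 0.4 × 0.66 = 0.852.
- Male excess of oesophageal adenocarcinoma 3:1 (Protocol 1.5). This is a general ratio, not one within Barrett's.
- For conversion in this cohort, the same sample-size text uses two thirds of the UK rate, about 1.5:1, for a mixed group: women, tongues of Barrett's, 1 cm segments, or age under 45.
- Sex-specific death rates and an HGD rate are not given. Death ratios below are assumptions, and HGD is not counted.

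The plan states no power or event figure for the gender comparison, so there is none to reproduce.

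**3. Composite hazard ratio, men to women**

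For a male:female ratio R and overall rate r, the female rate is r / (0.801R + 0.199) and the male rate is R times that. The composite HR is (male conversion + male death) / (female conversion + female death).

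- Conversion 3:1, death 1:1: (0.980 + 1.160) / (0.327 + 1.160) = 1.44.
- Conversion 1:1, death 2:1 (assumed): (0.850 + 1.288) / (0.850 + 0.644) = 1.43.

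| Conversion ratio | Death ratio (assumed) | Composite HR |
|---|---|---|
| 3 | 0.8 | 1.22 |
| 3 | 1.0 | 1.44 |
| 3 | 1.2 | 1.64 |
| 3 | 1.5 | 1.92 |
| 1 | 1.2 | 1.11 |
| 1 | 1.5 | 1.25 |
| 1 | 2.0 | 1.43 |

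Deaths make up 1.16 / (1.16 + 0.85) = 58% of these events, so the composite result depends heavily on the sex difference in mortality.

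**4. Could adenocarcinoma be compared by sex on its own?**

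Assume constant hazards and 8 years of follow-up. Events in each sex = N × (1 − exp(−8 × rate)). Two approximations, two-sided 5%:

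- (a) Φ(ln R / SE − 1.96), with SE = √(1/male events + 1/female events).
- (b) Schoenfeld: Φ(ln R × √(total events × 0.199 × 0.801) − 1.96).

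| Ratio R | Male / female events | Power (a) | Power (b) |
|---|---|---|---|
| 1.5 | 141 / 24 | 45% | 55% |
| 2 | 146 / 19 | 80% | 94% |
| 3 | 152 / 13 | 97% | >99% |

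Removing competing deaths (equal by sex) lowers these by up to about two percentage points. The two methods diverge because (b) splits events by numbers randomised, whereas (a) uses the much smaller expected count in women.

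**The case against.** The SAP is not out of line with every part of the protocol. It agrees with the synopsis, and the composite is a legitimate reading of conversion or survival taken as one outcome. A reader might infer that conversion alone is the question and that the planned analysis misses it. The documents do not support that: the objective refers to outcomes in general, SAP section 9 names conversion or survival, and generalisability is the SAP's stated reason for entering women. The composite answers part of the question.

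The adenocarcinoma risk-factor models are a natural place for a sex comparison, and Protocol 1.5 mentions the male excess in its sentence on clinical risk factors. This stands in part, because gender could be included but is not guaranteed.

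The near-equality of 1.44 and 1.43 depends on a death ratio chosen to produce it. It shows that confusion is possible, not that it is likely. Counting HGD would raise the conversion share.

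Finally, five endpoints each with logrank, AFT and Cox would make 15 gender analyses, and SAP 8.3 plans no multiplicity adjustment. That favours a restrained fix but does not justify leaving out protocol-listed endpoints without comment.

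**Conclusion.** The point holds as a mismatch between documents with a consequence for interpretation. Protocol section 3 lists five gender endpoints, whereas the synopsis and SAP 2.7 and 9 specify one. The composite alone cannot show whether a sex difference lies in conversion or in death. That conclusion follows from how the composite is defined and does not need the illustrative figures.

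Those figures rest on constant hazards, the plan's overall rates, HGD not counted and assumed sex-specific ratios. A reader might also infer that a separate adenocarcinoma analysis is assured of about 97% power. That needs 3:1 to apply within Barrett's, while the 0.85% rate used with it was built on the two-thirds assumption. At about 1.5:1, itself stated for a mixed group and not for women alone, power is roughly 45–55%. The separate estimates are worth having for attribution, but a null result on a component may be uninformative.

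This should be corrected, but it concerns a secondary objective and leaves the primary analysis untouched.

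**What to change.** In SAP 2.7 and section 9:

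- Keep the composite as the lead gender analysis.
- Add male–female models for all-cause mortality, adenocarcinoma, HGD and oesophageal cancer death, labelled supportive. Report time ratios or hazard ratios with 95% confidence intervals.
- For HGD, adenocarcinoma and oesophageal cancer death, use the competing-risks approach that section 9 already plans for treatment.
- Report oesophageal cancer death mainly as counts by sex plus an estimate with its interval, since events among 501 women are likely to be sparse.

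Align the gender endpoint in the protocol synopsis with section 3.

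The cost is SAP wording and re-used code. All four event times are already defined in SAP 2.7, and gender is recorded at randomisation (SAP 6.6). The downside is a few more unadjusted secondary comparisons, which the supportive label and emphasis on estimation should contain.
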